6.1.2.8 Tumor Tissue Collection and Correlative Studies: Blood and CSF Sampling

6.1.2.8.2 Tumor Tissue Collection

Submission of archival tumor tissue is optional in this study. If tumor tissue is available, exploratory analyses may be undertaken as detailed in section 4.1.5.2. If there is any leftover blood, the tissue will be stored for future research purposes if he/she consents to any separate tissue banking protocol. If not, the remaining tissue will be destroyed.

6.1.2.8.2. Blood collection for Correlative Studies

Additional biomarker research to identify factors important for pembrolizumab therapy as detailed in section 4.1.5.2, may be pursued. If there is any leftover blood, the blood will be stored for future research purposes if he/she consents to any separate tissue banking protocol. If not, the remaining blood will be destroyed.

6.1.2.8.3. CSF Sample collection

Patients will undergo a lumbar puncture using routine clinical care procedures to collect up to 10-15cc of CSF for research purposes, after routine clinical CSF is obtained. In patients with a CSF-access device such as an Ommaya reservoir or shunt reservoir, the study team may use this device to obtain CSF as an alternative to lumbar puncture. A CSF sample will be obtained during screening to obtain a "baseline" sample, and assess for eligibility based on CSF cytology. In patients who proceed with the study, repeat CSF samples will be obtained prior to administration of cycle 3 of therapy and 2-3 weeks after administration of cycle 4 (if last treatment, as end-of-treatment sample) or prior to cycle 5, if the patient is planned to receive cycle 5. The maximum number of lumbar punctures from an individual patient is four. In order to safely complete an LP for the acquisition of a CSF sample, patients must:

- a) Have an ECOG performance status < 2
- b) Have normal laboratory criteria as defined below:
- -Platelets >100,000/mcL[SEP]
- -PTT above institutional limits
- -INR above institutional limits
- c) No clinical or radiographic evidence of elevated intracranial pressure (such as papilledema, obstructive hydrocephalus, or signs of herniation).
- d) Not be taking blood-thinning products such as clopidogrel, low-molecular weight heparin, or coumadin.
- 5) For patients undergoing an LP, no history of LP complication such as hematoma, infection, herniation, or blood patch, and a complicated LP procedure in the past.

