2.0 TRIAL DESIGN

2.1 Trial Design

This is an open-label phase II study of pembrolizumab in patients with advanced solid tumors with leptomeningeal carcinomatosis (LMD). Patients may have received any number of prior therapies for their respective solid tumors, but must not have received prior anti-PD-1 therapy and developed progressive disease. Approximately 18 subjects in this study will receive pembrolizumab at a dose of 200mg intravenously (IV) every 3 weeks (Q3W) for 4 doses. In patients who derive clinical benefit from therapy, pembrolizumab may be continued until documented disease progression, unacceptable adverse event(s), intercurrent illness that prevents further administration of treatment, investigator's decision to withdraw the subject, subject withdrawal of consent, noncompliance with trial treatment or procedure requirements, or for administrative reasons.

This study aims to determine if pembrolizumab can cause a radiologic, cytologic or clinical response in the CNS in patients with advanced solid tumors with LMD. The primary endpoint is thus central nervous system (CNS) response, defined either as radiologic response (reduction in size of LMD on gadolinium-enhanced MRI imaging of the brain and total spine including T1- weighted, T2-weighted, fluid attenuated inversion recovery and post-gadolinium sequences)

and/or cytologic response (conversion of positive to negative CSF cytology on 2 consecutive samples) and/or clinical response (Table 8), as detailed in the section 4.1.5.1.1 and 6.1.2.7.

Secondary endpoints will include progression-free survival (PFS), overall survival (OS), and safety.

Patients will undergo routine screening investigations including CBC, CMP, urine, pregnancy test, standard radiologic imaging of the body (CT), cerebrospinal fluid (CSF) sampling for cytology, and a pre-treatment gadolinium-enhanced MRI scan of the brain and total-spine. During the trial, patients will be monitored with a clinical visit, adverse event assessment and routine laboratory tests at the time of each dose of pembrolizumab. Patients will have a CSF sample taken, blood draws, radiologic imaging of the body (CT), and a contrast-enhanced MRI scan of the brain and total-spine after 2 and 4 cycles of therapy for response assessment and correlative studies. In patients with a CSF sample that demonstrates negative cytology, an additional confirmatory CSF sample will be obtained 3 weeks after the first negative CSF cytology sample.

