5.0 TRIAL FLOW CHART

Table 7: Study Flow Chart

Trial Period:	Screenin g Phase	Treatment Cycles ^a						End of Treatment		Post-Treatment			
	Study Screening					showi	s 5+ on ng clin	nical b	enefit.				Survival
Treatment Cycle/Title:	(Visit 1)	1	2	3	4	5	6	7	8	Discon ⁹	Safety Follow-up	Follow Up Visits	Follow- Up
Scheduling Window (Days):	-28 to -1	± 3 ⁸	± 3	± 3	± 3	± 3	± 3	± 3	± 3	At time of discon	30 days post discon	Every 6-9 weeks post discon	Every 12 weeks
Administrative Procedures													
Informed Consent	X												
Inclusion/Exclusion Criteria	X												
Demographics and Medical History	X												
Prior and Concomitant Medication Review	X	X	X	X	X	X	X	X	X	X	X	X	
Post-study anticancer therapy status	X									X	X	X	
Survival Status													X
Clinical Procedures/Assessments													
Review Adverse Events	X	X	X	X	X	X	X	X	X	X	X	X	
Full Physical Examination	X									X			
Directed Physical Examination		X	X	X	X	X	X	X	X				
Vital Signs, Weight	X	X	X	X	X	X	X	X	X	X			
Oxygen saturation	X	X	X	X	X	X	X	X	X	X			
ECOG Performance Status	X	X	X	X	X	X	X	X	X	X			
Pembrolizumab Administration		X	X	X	X	X	X	X	X				
Laboratory Procedures/Assessments: anal	ysis perforr	ned by	LOCA	L labo	ratory								
Pregnancy Test – Urine or Serum β -HCG ¹	X	X	X	X	X	X	X	X	X	X	X		
PT/INR and aPTT	X												
CBC with Differential	X	X	X	X	X	X	X	X	X	X	X		

Trial Period:	Screenin g Phase	Treatment Cycles ^a							End of T	reatment	Post-Treatment		
	Study Screening					showi	s 5+ on ng clin continue	nical b	enefit.		G. C.	F 11 H	Survival
Treatment Cycle/Title:	(Visit 1)	1	2	3	4	5	6	7	8	Discon ⁹	Safety Follow-up	Follow Up Visits	Follow- Up
Scheduling Window (Days):	-28 to -1	± 3 ⁸	± 3	± 3	± 3	± 3	± 3	± 3	± 3	At time of discon	30 days post discon	Every 6-9 weeks post discon	Every 12 weeks
Comprehensive Serum Chemistry Panel	X	X	X	X	X	X	X	X	X	X	X		
Urinalysis	X												
TSH ²	X		X		X		X		X	X			
Hepatitis B, C, HIV	X												
Efficacy Measurements													
MRI Brain and Full-spine with contrast	X			X ³		X^3				X^3		X^4	
CT chest/abdomen/pelvis with contrast	X			X ³		X^3				X^3		X^4	
Tumor Biopsies/Archival Tissue Collection	ı/Correlativ	e Studi	ies Blo	od									
Archival Tissue Collection ⁵	X												
Blood collection for Genomics	X			X		X				X			
Blood collection for Immune correlates	X			X		X				X			
CSF sample acquisition ⁶	X			X		X ⁷				X^7			
CSF sample correlates	X			X		X^7				X^7			

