6.1.3 Laboratory Procedures/Assessments

Details regarding specific laboratory procedures/assessments to be performed in this trial are provided in the trial flow chart.

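### Every lumbar puncture is conditional on PTT and INR, but these are scheduled only at screening (about 6 to 14 weeks before the planned on-study taps), and both criteria are printed the wrong way round

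*Combined protocol and SAP*

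**What the plan says.** Section 6.1.2.8.3 sets out what a patient needs before an LP: "In order to safely complete an LP for the acquisition of a CSF sample, patients must". Condition (b) is headed "Have normal laboratory criteria as defined below" and lists a platelet threshold, then "PTT above institutional limits" and "INR above institutional limits". The same section plans CSF at screening, before cycle 3, and after cycle 4 or before cycle 5. It also sets a cap: "The maximum number of lumbar punctures from an individual patient is four".

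Section 2.1 adds a conditional tap for patients whose cytology turns negative: "an additional confirmatory CSF sample will be obtained 3 weeks after the first negative CSF cytology sample".

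On laboratory timing, Section 6.1.3 says: "Details regarding specific laboratory procedures/assessments to be performed in this trial are provided in the trial flow chart". In that chart (Section 5.0, Table 7) the row "PT/INR and aPTT" has one mark, in the screening column. CBC and the chemistry panel are marked at screening, every cycle, discontinuation and the safety visit. Table 10 names PT (INR) and aPTT but assigns them to no visit. The confirmatory tap has no column or row in Table 7.

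**The concern.** The protocol makes coagulation status a condition of a safe LP and lists hematoma among LP complications, yet its schedule produces no current PTT or INR for any on-study LP. These taps are required by the protocol and include CSF drawn for research.

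A screening value cannot be assumed to persist. Table 5 anticipates hepatic toxicity from the drug, and Table 3 admits patients with liver metastases and AST/ALT up to 5 x ULN.

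Separately, the rule as printed would require abnormal clotting before an LP. Table 3 does not supply the missing limit, because it admits patients with INR/PT and aPTT up to 1.5 x ULN. A patient can therefore be eligible and still above normal, and only Section 6.1.2.8.3 can say whether the LP may go ahead.

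What is at stake is patient safety. Sections 4.1.5.1.1 and 7.2.4 allow CNS response to be scored by MRI or clinical criteria when CSF is missing, so the primary endpoint does not depend on this.

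**Working it through.** **Inputs**

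- Screening laboratory tests fall within 10 days before the first dose (Sections 4.2.6 item 12, 6.1.3.1 and 6.1.5.1.1), so the lead time is 0 to 10 days.
- Cycles last 21 days (Table 4), with dosing allowed 3 days either side (Section 4.3.2).
- The planned on-study taps are before cycle 3, and then either before cycle 5 or at end of treatment. The end-of-treatment tap is 2 to 3 weeks after cycle 4 in Section 6.1.2.8.3 but within 2 weeks of the last dose in Table 7 footnote 7. Both timings are worked below.
- The confirmatory tap is 21 days after the first negative cytology (Section 2.1).
- The LP cap is 4, and the planned sample is 18 patients.

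**Calendar check.** Cycle k Day 1 falls (k - 1) x 21 days after the first dose: cycle 3 on day 42, cycle 4 on day 63, cycle 5 on day 84. Four cycles take 4 x 3 = 12 weeks, which matches the 12-week anchor in Section 7.2.1.

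**Age of the last scheduled result** = tap day + lead time (0 to 10 days). The last column widens this by 3 days at each end.

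| Tap | Tap day | Age, days | Age, weeks | With the 3-day window, weeks |
|---|---|---|---|---|
| Before cycle 3 | 42 | 42-52 | 6.0-7.4 | 5.6-7.9 |
| End of treatment, footnote 7 | 63-77 | 63-87 | 9.0-12.4 | 8.6-12.9 |
| End of treatment, Section 6.1.2.8.3 | 77-84 | 77-94 | 11.0-13.4 | 10.6-13.9 |
| Before cycle 5 | 84 | 84-94 | 12.0-13.4 | 11.6-13.9 |
| Confirmatory, after the pre-cycle-3 tap | 63 | 63-73 | 9.0-10.4 | 8.6-10.9 |
| Confirmatory, after the later tap | 84-105 | 84-115 | 12.0-16.4 | 11.6-16.9 |

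The last row adds 21 days to the earliest (63) and latest (84) later tap. The two planned on-study taps together span about 6 to 14 weeks. If the general 28-day screening window applied to these tests instead of the 10-day rule, the upper end for the planned taps would be 84 + 28 = 112 days (16.0 weeks), or 115 days (16.4 weeks) with the window.

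**LPs against tests.** One screening LP plus two planned on-study LPs makes 3, and the cap of 4 leaves room for 4 - 3 = 1 confirmatory LP. On-study LPs number at most 4 - 1 = 3, against 0 scheduled coagulation tests after screening.

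**Wording check.** The heading of (b) asks for normal values; the two coagulation lines under it ask for values above the limits. The error lies in the word used, so it is not a comparison sign lost in reading the PDF.

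**The case against.** The strongest reply is that condition (b) applies at the time of each LP, so whoever performs the tap must establish then that it is met. Nothing says the screening value suffices. Section 6.1 permits unscheduled procedures when clinically necessary, and Section 6.1.2.8.3 has LPs done as in routine care, so a site may well test beforehand. The other conditions are already refreshed: ECOG, platelets and medication review at every cycle, and MRI around the planned taps. Condition (d) bars LP in patients on blood thinners, and some patients will have a CSF-access device. The inversion is an obvious slip that few clinicians would follow, and no harm is quantified.

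Part of this stands. The 6 to 14 weeks is the age of the last scheduled result; the age of the result actually used at a tap is unknown. Literal misreading is unlikely. The residual risk is a new coagulopathy that nobody suspects or tests for, and the documents give no rate for it.

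The rest does not close the gap. Unscheduled testing is discretionary, the reference to routine care names no coagulation test, and CBC, liver tests and medication review are indirect. None of these requires a current PTT or INR. Section 6.1.3.1 also says tests need not be repeated after treatment ends if values are in the normal range, so nothing prompts a test at the end-of-treatment tap. A mandatory safety criterion should not rely on staff disregarding its wording.

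**Conclusion.** The concern holds. Each patient has one scheduled coagulation result against up to four LPs, and up to three on-study LPs have none of their own. The last scheduled result is about 6 to 8 weeks old before cycle 3, about 9 to 14 weeks old at the end-of-treatment or pre-cycle-5 tap, and between about 9 and 17 weeks old at a confirmatory tap. Both printed coagulation criteria are the reverse of what their heading asks for.

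The ages assume the 10-day screening rule, four doses given on schedule and no unscheduled test; dose delays would lengthen them. The number of patients put at risk cannot be estimated from the documents. The sample size, confidence intervals and endpoint evaluability are unaffected. The change should be made because the printed safety rule is wrong and the correction is cheap.

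**What to change.** 1. In Section 6.1.2.8.3, change the two criteria to PTT and INR not above institutional limits. State that conditions (b) and (d) are confirmed on current results and the current medication list before each LP.
2. In Table 7, schedule PT/INR and aPTT within 72 hours before each on-study LP (cycle 3, and cycle 5 or discontinuation). This matches the interval that Section 6.1.3.1 already allows for pre-dose tests, and the result would then be at most 3 days old.
3. Add the confirmatory tap to Table 7 with the same tests.

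The wording correction costs nothing. The added tests number at most 18 x 2 = 36 for the planned taps plus 18 x 1 = 18 for confirmatory taps, 54 in all, and fewer with deaths, progression or CSF devices. Most fit existing draws: a confirmatory tap after the pre-cycle-3 sample falls on day 63 (cycle 4), and one after the pre-cycle-5 sample on day 84 + 21 = 105 (cycle 6). One after an end-of-treatment sample falls 3 to 6 weeks after the last dose and may need its own draw. The downside is that an occasional tap will be postponed or not done.

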Hepatic					
Serum total bilirubin	≤ 1.5 X ULN OR				
	Direct bilirubin ≤ ULN for subjects with total bilirubin levels > 1.5 ULN				
AST (SGOT) and ALT (SGPT)	≤ 2.5 X ULN OR ≤ 5 X ULN for subjects with liver metastases				
Albumin	>2.5 mg/dL				
Coagulation	·				
International Normalized Ratio (INR) or Prothrombin Time (PT)	≤1.5 X ULN unless subject is receiving anticoagulant therapy as long as PT or PTT is within therapeutic range of intended use of anticoagulants				
Activated Partial Thromboplastin Time (aPTT)	≤1.5 X ULN unless subject is receiving anticoagulant therapy as long as PT or PTT is within therapeutic range of intended use of anticoagulants				
^a Creatinine clearance should be calculated	per institutional standard.				

- 13. Female subject of childbearing potential should have a negative urine or serum pregnancy within 72 hours prior to receiving the first dose of study medication. If the urine test is positive or cannot be confirmed as negative, a serum pregnancy test will be required.
- 14. Female subjects of childbearing potential (Section 4.8.2) must be willing to use an adequate method of contraception as outlined in Section 4.8.2 Contraception, for the course of the study through 120 days after the last dose of study medication.

Note: Abstinence is acceptable if this is the usual lifestyle and preferred contraception for the subject.

15. Male subjects of childbearing potential (Section 4.8.2) must agree to use an adequate method of contraception as outlined in Section 4.8.2- Contraception, starting with the first dose of study therapy through 120 days after the last dose of study therapy.

Note: Abstinence is acceptable if this is the usual lifestyle and preferred contraception for the subject.

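### The lumbar-puncture safety list has its PTT and INR criteria reversed: it asks for values above institutional limits where normal values are meant

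*Combined protocol and SAP*

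**What the plan says.** Section 6.1.2.8.3 introduces its LP list with "In order to safely complete an LP for the acquisition of a CSF sample, patients must", so every entry is a requirement the patient has to meet. Item b is headed "Have normal laboratory criteria as defined below" and has three bullets:

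- "Platelets >100,000/mcL"
- "PTT above institutional limits"
- "INR above institutional limits"

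Two other entries in the list bear on bleeding. Item d requires that patients "Not be taking blood-thinning products such as clopidogrel, low-molecular weight heparin, or coumadin". The last item asks for "no history of LP complication such as hematoma, infection, herniation, or blood patch".

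Elsewhere, the coagulation rows of Table 3 (section 4.2.6) cap INR/PT and aPTT for trial entry at "≤1.5 X ULN unless subject is receiving anticoagulant therapy". Exclusion criterion 22 in section 4.2.7, which concerns mass effect from brain metastases, refers to section 6.1.2.8.3 for LP contraindications.

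**The concern.** A prolonged PTT or a raised INR signals impaired clotting, which is a reason to withhold an LP. Here both appear as conditions for going ahead. The header of item b points one way and two of its three bullets point the other. The header also hands the definition of normal to those bullets, so it does not formally override them.

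What is at stake is the correctness of a procedural safety rule. CSF is sampled at screening, before cycle 3, and after cycle 4 or before cycle 5, with up to four LPs per patient. Part of each collection is for research. These bullets are the only place where the protocol sets a clotting limit for those procedures. No statistical quantity depends on them.

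**Working it through.** No arithmetic beyond a line count applies. The check is whether any reading of the text makes the two bullets correct.

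**Step 1: requirements or exclusions?** The lead-in says what patients must satisfy. If item b were instead a list of exclusions, the platelet bullet would bar an LP in anyone with more than 100,000/mcL, which is absurd. So the sub-list states requirements.

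**Step 2: what item b does when applied literally.** Take a patient whose platelets exceed 100,000/mcL:

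| PTT and INR | As written | As the header intends |
|---|---|---|
| Both within limits | Fails | Passes |
| Both above limits | Passes | Fails |
| One above, one within | Fails | Fails |

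The written rule gives the wrong answer in the first two rows, which are the clear-cut cases.

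**Step 3: the rest of the list.** Five statements bear on bleeding: platelets, PTT, INR, blood-thinning drugs (item d), and a history of LP hematoma (part of the last item).

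- Within item b: 2 of 3 bullets are reversed (PTT, INR) and 1 is in the safe direction (platelets).
- Across the list: 2 of 5 are reversed, and 5 − 2 = 3 are in the safe direction.

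The three correct statements all aim to keep patients at risk of bleeding away from LP, so the two reversed ones are out of line with the list's purpose.

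**Step 4: is the rule stated correctly anywhere else?** Table 3 is the only other clotting limit, and it cannot stand in for an LP rule:

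- It governs entry to the trial, not each LP.
- Its ceiling is 1.5 × ULN, so a patient modestly above normal may enroll yet should fail a requirement for normal values.
- It makes an exception for patients on anticoagulants, while item d of the LP list bars patients taking blood thinners.

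Exclusion criterion 22 sends the reader back to this same section and concerns mass effect, so it supplies no clotting limit.

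**Step 5: is it an artefact of text extraction?** That is unlikely. The word giving the direction is spelled out in full in both bullets; it is not a symbol that could have been lost or misread.

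**The case against.** The strongest reply is that this is a typographical slip, most likely a dropped negative, and that nobody would act on it. The header asks for normal values, item d bars blood thinners, and section 6.1.2.8.3 says LPs follow usual clinical practice. A clinician would not refuse an LP because the INR is normal or proceed because it is raised. At baseline, Table 3 screening largely covers the same ground. All of this stands. It is why the point is minor and why no harm or number of affected patients is claimed. It does not make the text right, and Table 3 does not reach the on-treatment LPs.

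The line counts can also be criticized: they describe text, not effect, and the grouping into five bleeding-related statements is a reviewer's choice. That is fair. They show only how far the error extends.

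Two further observations are accurate but lie outside this point. First, the flow chart (Table 7) schedules PT/INR and aPTT at screening only, so even corrected bullets would have no scheduled test behind them at later LPs. Second, a limit set at normal is stricter than Table 3, so a patient at, say, 1.3 × ULN could enroll but not have an LP. The existing header already implies that gap; the correction does not create it.

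**Conclusion.** The concern holds. Two of the three laboratory bullets in item b of section 6.1.2.8.3 are reversed as written, and no other text in the protocol gives the LP clotting rule correctly. The conclusion rests on the wording alone, with no numerical assumption. It is best described as a drafting error in an operative safety criterion rather than a weakness of design. Severity is minor because the intended direction is easy to infer and would probably be followed. The sample size, the primary endpoint and its confidence intervals, and the analysis are untouched.

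**What to change.** In section 6.1.2.8.3, item b, reword the two bullets so that PTT and INR are each required to be not above (within) institutional limits. Leave the platelet bullet and the other items as they are. The cost is a few words in two bullets, with no change to eligibility, LP schedule, laboratory testing, endpoint, sample size or analysis.

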6.1.3 Laboratory Procedures/Assessments

Details regarding specific laboratory procedures/assessments to be performed in this trial are provided in the trial flow chart.

